10.14 ECG

An ECG will be recorded according to local procedures with the purpose of identifying possible subjects with long QT-syndrome and potential QT prolongation during the study. Subjects with long QT syndrome cannot be enrolled in the trial. In case of QT prolongation onset during the trial subjects must be discontinued, QT, QTc and pulse will be recorded in the e-CRF.

10.15 Laboratory Tests

Blood samples will be taken using standard venepuncture techniques. Altogether approximately 25 ml blood will be drawn from each subject.

The following laboratory variables will be measured:

Haematology:

Erythrocytes, haemoglobin, haematocrit, leukocytes, neutrophils, eosinophils, basophils, lymphocytes, and monocytes.

Blood chemistry:

Creatinine, urea, sodium, potassium, calcium, alanine aminotransferase (ALAT), albumin, bilirubin, alkaline phosphatase, lactate dehydrogenase (LDH), C-reactive protein (CRP), thyroid stimulation hormone (TSH), T3 and T4.

The clinical laboratory values will be reported to the investigator or a delegate by the laboratory and he/she must review them for significance.

These blood samples are taken as standard part of monitoring patients suffering from HG in order to identify possible electrolyte derangement or other conditions causing symptoms similar to HG. Specifically relevant to this trial are ALAT, ASAT and creatinine since subjects might be excluded from the trial if these are elevated.

Plasma-mirtazapine and -ondansetron will be measured in the mirtazapine- and ondansetron-groups, after the last subject has been unblinded. The purpose of this analysis is explorative.

Biobank:

Blood samples will be stored at -80°C , so that subsequent analysis of newly discovered relevant markers can be performed without further discomfort to the patient. The blood samples will be stored for 10 years and will then be destroyed.

10.16 Questionnaires

Questionnaires on PUQE-24 score, nausea VAS, number of daily vomiting episodes, EQ-5D-5L (health related quality of life), NVPQOL (nausea and vomiting of pregnancy quality of life), HELP (hyperemesis level prediction), modified PSQI (Pittsburg sleep quality index), patient satisfaction with treatment VAS, possible patient consideration of termination of pregnancy and possible side effects and AEs, sick leave, hospitalisation and amount of i.v. fluids will be filled out online directly in the e-CRF by subjects at Visit 1, 2 and 3. Subjects will daily fill out online questionnaires directly in the e-CRF on PUQE-24 score, nausea VAS, number of daily vomiting episodes, time of IMP-administration (and possible re-administration) use of rescue medication as well as possible side effects and AEs during the trial.

Subjects will be prompted to continue daily online registration of possible side effects and AEs until five days after end of intervention.

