Changes in concomitant medication		x		x	x		
Vital signs (Height ¹ , weight, BP and pulse)	x	x		x	x		
Physical examination	x						
Ultrasound	x						
PUQE 24-score	x	x	x	x	x		
Nausea VAS, daily vomiting episodes		x	x	x	x		
Rescue medication			x	x	x		
NVPQOL, HELP, EQ-5D, modified PSQI		x		x	x		
Patient consideration of termination of pregnancy		x		x	x		
Patient satisfaction with treatment VAS				x	x		
Sick leave				x	x		
Hospitalization				x	x		
I.v. fluids				x	x		
Dosage increase				x			
Continuation of trial medication					x		
Side effects, adverse events			x	x	x	x	
Blood samples	x	x		x	x		
Urine sample	x						
ECG	x			x	x		
Randomisation		x					
Dispense of trial medication		x		x			
Drug accountability				x	x		
Pregnancy Outcome							x

1) Height only at screening

CONFIDENTIAL

3. Background / Rationale

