9.1 Administration of Trial Products

Each subject will be randomly assigned to receive mirtazapine (IMP1), ondansetron (IMP2) or placebo. Please refer to figure 1 on page 17 for a visual on the trial design.

Trial medication will be provided by Glostrup Apotek in accordance with GMP. IMP1, IMP2 and placebo will be similar in appearance, smell and taste due to the IMPs being encapsulated in gelatine. In the placebo group the medication will be an empty gelatine capsule.

At Visit 1 on Day 0 each subject will receive two containers with sufficient medication for 10 days. One container will be labelled 'Morning' and one will be labelled 'Bedtime' to be administered orally in the morning and at bedtime for the first week (until Visit 2 on Day 7(+/-1)). Administration will start at bedtime of Day 0.

Thus, during the first week of intervention there will be two administrations of trial medication daily.

At Visit 2, two new containers with sufficient medication for 10 days will be administered. If dosage increase is not desired administration will proceed unchanged.

If a dosage increase is desired the number of daily administrations will go from two to four. One container will then be labelled 'Morning, noon and afternoon' and will be administered orally in the morning, at noon and late afternoon or early evening. The other container labelled 'Bedtime' will be administered only at bedtime.

In case a subject vomits within 45 minutes after administration of trial medication the subject will have to administer a new dosage as described in the folder 'Praktisk information om forsøgsmedicinen'.

If a subject runs out of trial medication before the next visit due to extra administrations because of vomiting, the subject must contact the investigator as described in the folder 'Praktisk information om forsøgsmedicinen'.

The folder 'Praktisk information om forsøgsmedicinen' will be handed out with the trial medication. Patients are encouraged to register time of administration and possible vomiting episodes within 45 minutes after administration in the folder.

CONFIDENTIAL

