9.2 Mirtazapine: IMP1

In the mirtazapine group, the 'Morning' medication will contain placebo and the 'Bedtime' medication dispensed at Visit 1 will contain mirtazapine 15 mg. Thus, the subjects in this group will initially receive treatment with

- Placebo oral tablet in the morning and
- Mirtazapine 15 mg oral tablet at bedtime.

The medication dispensed at Visit 2 on day 7(+/-1) will be the same and administration will remain unchanged in week 2 if dosage increase is not desired.

If dosage increase is desired at Visit 2 the 'Morning, noon and afternoon/evening' medication will be unchanged and still contain placebo. However, the 'Bedtime' medication dispensed will contain mirtazapine 30 mg as opposed to 15 mg in week 1. Thus, the treatment in the second week will be

- Placebo oral tablet in the morning, at noon and late afternoon/early evening and
- Mirtazapine 30 mg oral tablet at bedtime.

Mirtazapine is an antidepressant known to have antiemetic and appetite-stimulating effect. It is an alfa2-receptor antagonist, an antagonist on several serotonin-receptors (5HT_{2A}, 5HT_{2C} and 5HT₃) and on one histamine-receptor (H₁).

Recommended dosage is 15-30 mg daily initially and 15-45 mg daily as maintenance dosage, preferably administered once daily before bedtime.

Peak plasma-concentration is reached within 2 hours after oral administration. Elimination half-life is 20-40hours and time to reach steady state is 3-4 days.

Side effects:

- >10% : Increased appetite, weight gain, dry mouth, headache, sedation and somnolence.
- 1-10%: Diarrhea, obstipation, vomiting, orthostatic hypotension, peripheral edema, arthralgia, myalgia, back pain, abnormal dreams, anxiety, drowsiness, confusion, dizziness, tremor and rash.
- 0,1-1%: Hypotension, agitation, hallucinations, mania, motoric unrest, paresthesia, syncope.
- 0,01-0,1%: Pancreatitis, aggressiveness, myoclonia.
- Not known: Edema, eosinophilia, bone marrow depression, hyponatremia, rhabdomyolysis, dysarthria, oral paresthesia, serotonin syndrome, suicidal thoughts or behavior, bullous dermatitis, erythema multiforme, Stevens-Johnsons syndrome, toxic epidermal necrolysis, urine-retention.(37)

There is data on 1963 mirtazapine-exposed pregnant women without higher incidence of congenital malformations(32-35).

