10.1 Visit Schedule

Visit ID	Procedures to be performed at the visit
Screening Visit Day -2-0	Obtain written informed consent for the trial before any other trial procedures are performed Assess compliance with inclusion and exclusion criteria Obtain demographic data Record medical history Record use of relevant previous medications and concomitant medication Record PUQE-24 score Record pre-pregnancy weight Measure weight Measure height Measure vital signs Perform physical examination Perform ultrasound scan to confirm gestational age and singleton pregnancy, if there is no record of such in the medical journal from within 4 four weeks prior to visit Collect blood samples Record ECG to rule out long QT-syndrome Schedule date for next visit.
Visit 1 (Randomisation) Day 0 Baseline values recorded	Re-assess compliance with inclusion and exclusion criteria Record changes to concomitant medication Record PUQE-24 score Record nausea VAS Record number of daily vomiting Record EQ-5D, NVPQOL, HELP and modified PSQI Record possible patient consideration of termination of pregnancy Measure weight Measure vital signs Collect blood samples Randomise the subject Instruct the subject on how to use the IMP Dispense IMP, rescue medication and B-kombin to the subject (sufficient medication for 10 days) Schedule date for next visit
Visit 2 Day 7	Re-assess compliance with inclusion and exclusion criteria Record changes to concomitant medication and including rescue medication Record PUQE-24 score Record nausea VAS Record number of daily vomiting Record EQ-5D, NVPQOL, HELP and modified PSQI

CONFIDENTIAL

Visit ID	Procedures to be performed at the visit
	Record patient satisfaction with treatment VAS Record possible patient consideration of termination of pregnancy Record sick leave Record possible hospitalization Record possible administration of i.v. fluids Record side effects Assess AEs occurring since the last visit Record use of rescue medication Record desire for dosage increase Measure weight Measure vital signs Record ECG Collect blood samples Collect used IMP and rescue medication and perform drug accountability and compliance check Dispense IMP, rescue medication and B-kombin to the subject (sufficient medication for 10 days) Schedule date for next visit

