6.9 Timing of outcome assessments

Baseline characteristics will be assessed on Day 0.

PUQE-24 score, daily vomiting episodes, nausea VAS, administration of IMP and rescue medication and possible side effects will be registered daily by subjects via online questionnaires.

NVPQOL, HELP, EQ-5D, PSQI, patient satisfaction with treatment, patient consideration of termination of pregnancy, number of days on sick leave, amount of treatments with i.v.-fluids, number of days of hospitalisations and weight change will be registered via online questionnaires at Visit 1, 2 and 3.

Request for continuation of trial medication will be registered via online questionnaire at Visit 3.

The visits on Day 7(Visit 2) and Day 14(Visit 3) can be scheduled for day 6-8 and day 13-15 respectively.

Possible treatment failure will be registered when it occurs.

Birth outcome will be registered one month after delivery.

7. Statistical Principles

CONFIDENTIAL

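### Protocol 10.16 places the side-effect questionnaire at Visit 1, but the schedule starts it after the first dose, so patient-reported complaints already present cannot be told from new ones

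*Protocol*

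**What the plan says.** Protocol 10.16 names the online questionnaires that subjects complete at visits. The list includes "possible side effects and AEs, sick leave, hospitalisation and amount of i.v. fluids will be filled out online directly in the e-CRF", and the same sentence gives the time of completion as "by subjects at Visit 1, 2 and 3". Daily online entries, which also cover side effects and AEs, come on top of this.

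The other passages on timing differ:

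- **Protocol section 2 (Trial Schedule).** The row "Side effects, adverse events" is blank at Screening and Visit 1. It is marked for the Day 1-14 online questionnaire, Visits 2 and 3, and Day 15-20. The SAP section 2 flowchart is also blank at Screening and Visit 1.
- **Protocol 10.1 (Visit Schedule).** The Visit 1 list has no side-effect or AE item. It runs, for example, "Record possible patient consideration of termination of pregnancy Measure weight Measure vital signs Collect blood samples Randomise the subject". The first visit list with such an item is Visit 2: "Record side effects Assess AEs occurring since the last visit".
- **Protocol 9.1.** "Administration will start at bedtime of Day 0".
- **SAP 6.9.** "possible side effects will be registered daily by subjects via online questionnaires", with no pre-dose entry named.
- **Protocol 10.2.** For specific timing, the reader is sent to the visit schedule.

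Protocol 9.2 gives the mirtazapine side effects expected in more than 10% as "Increased appetite, weight gain, dry mouth, headache, sedation and somnolence". Protocol 9.3 lists headache above 10% for ondansetron and constipation at 1-10%. SAP 9.4 (Harms) only refers to the protocol for definitions and reporting. It gives no comparison by arm and no definition of a new or worsened side effect.

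**The concern.** Several of the listed harms, such as headache, dry mouth and drowsiness, could plausibly be present in women with hyperemesis before they take a capsule. The documents give no prevalence, so this is an assumption. PUQE-24, nausea VAS, vomiting, quality of life and sleep are all recorded at Visit 1 and so have a pre-dose reference. Patient-reported side effects have one only if sites follow 10.16 rather than the schedule, and the schedule is where 10.2 sends them.

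Without that reference, a woman who had a headache on Day 0 and reports it on Day 1 looks the same as one whose headache began after the first dose. Protocol 3.3 gives systematic collection of efficacy and side effects as part of the ethical case for the trial, so it matters how well these data can be read. A pre-dose answer that was not collected cannot be obtained later.

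**Working it through.** **1. Timing.** The only visits before the first dose are Screening and Visit 1. Under both flowcharts and the 10.1 list, neither includes the side-effect questionnaire. The first dose is at bedtime of Day 0 and the first scheduled entry is on Day 1, so the first answer is post-dose. Under 10.16 read literally, there would be an answer at Visit 1. The two cannot both be followed.

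**2. What the other rules cover.** Protocol section 11 records AEs from consent and has a physician assess causality. Protocol 11.1 excludes pre-existing conditions documented as medical history unless they worsen. Protocol 10.9 limits medical history to what the investigator considers relevant, but defines concomitant disease as any illness present at the start. These rules help with physician-assessed AEs. None of them is a pre-dose record of the questionnaire the subject later completes daily.

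**3. The plan's own figures.** The documents give no figure for side effects. Their one design calculation reproduces: 2 × (3 × (2.241 + 0.842) / 2)² = 42.8 per group, and 42.8 / 0.75 = 57.0, matching the stated 57, rounded up to 60. It is used here only for the arm size.

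**4. Effect of having no pre-dose answers.** Let b be the share with the complaint before dosing and r the new-onset risk among the rest. Assume that pre-existing complaints persist and are reported.

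- Crude count: b + (1 − b) × r
- New onset, all randomised as denominator: (1 − b) × r
- Risk difference between arms under either count: (1 − b) × (r₁ − r₀)

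Assumed r: 15% on placebo, 40% on mirtazapine. Power is exact, two-sided Fisher at 5%, 60 per arm.

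| b | Crude, placebo vs active | New onset, placebo vs active | Difference, both counts | Crude risk ratio | New-onset risk ratio | Crude power | New-onset power |
|---|---|---|---|---|---|---|---|
| 10% | 23.5% vs 46.0% | 13.5% vs 36.0% | 22.5 points | 1.96 | 2.67 | 67% | 77% |
| 30% | 40.5% vs 58.0% | 10.5% vs 28.0% | 17.5 points | 1.43 | 2.67 | 43% | 61% |
| 50% | 57.5% vs 70.0% | 7.5% vs 20.0% | 12.5 points | 1.22 | 2.67 | 23% | 41% |

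Example at b = 30%: crude placebo 0.30 + 0.70 × 0.15 = 0.405; crude active 0.30 + 0.70 × 0.40 = 0.580; ratio 0.580 / 0.405 = 1.43. New onset: 0.70 × 0.15 = 0.105 and 0.70 × 0.40 = 0.280; ratio 2.67. Both differences are 0.175.

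What changes between the counts is the level of the rates, the ratio and the power. The absolute difference does not change.

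**The case against.** The strongest reply is that there is little real conflict. Protocol 10.2 says the visit schedule governs timing, and the 10.16 sentence may be a loose pooled list. It also puts satisfaction with treatment, sick leave, hospitalisation and i.v. fluids at Visit 1, where the schedule has none of them, and satisfaction cannot be rated before treatment. SAP 6.9 uses similar shorthand when it places weight change at Visits 1, 2 and 3. This stands. A reader might infer from 10.16 that a pre-dose side-effect baseline was intended and then dropped, but the documents do not show that. Letting the schedule govern settles which text to follow, but it also confirms that no pre-dose answer is collected.

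The second reply is that pre-existing complaints are already handled through recording from consent, the medical-history exclusion and causality assessment. That largely answers the point for physician-assessed AEs, and it would be wrong to say that every complaint from Day 1 counts as an AE. It answers it only in part for patient-reported side effects.

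The third reply concerns the illustration, and its limits are fair. The prevalences are assumed. At 5% pre-existing, power is 76% against 80%, a small loss. Side effects are not among the listed endpoints and no harms test is planned, so the power belongs to a comparison the plan does not state. The figures count new onset only, while a new-or-worsened definition would also count worsening. They do not represent constipation on ondansetron, listed at 1-10%.

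**Conclusion.** The passages conflict, and following the schedule leaves patient-reported side effects with no pre-dose reference. The consequence is inflated rates in every arm, risk ratios pulled towards 1 and lower power. Under the assumed rates the power loss runs from 10 percentage points at 10% pre-existing to 18 at both 30% and 50%. The direction follows from the algebra; the size rests on prevalences the documents do not give and on pre-existing complaints persisting and being reported.

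Two stronger readings are tempting and are not supported. One is that the gap favours a particular arm: randomisation makes pre-existing complaints equally likely in all arms, so this is attenuation. The other is that counting new onset would restore a larger absolute difference: among all randomised the difference is the same by either count, for example 17.5 points at 30% pre-existing.

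This is a minor point about the quality of the harms data. It does not touch the primary analysis.

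**What to change.** Reconcile Protocol 10.16, the Visit 1 list in 10.1 and both flowcharts so that the existing side-effect questionnaire is completed once at Visit 1, before the first dose. While editing 10.16, separate the items meant for Visit 1 from those that make sense only at Visits 2 and 3. In SAP 6.9, name the Visit 1 entry as the reference. In SAP 9.4, state that patient-reported side effects are compared by arm as new or worsened relative to that entry, with the crude count alongside.

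The cost is one more completion of an existing online form, at a visit that already has questionnaires, and a few sentences of text. The downside is a few minutes of patient time.

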10.17 Treatment failure

Treatment failure will be registered if a subject decides to discontinue the trial because of insufficient symptom relief. Time of treatment failure will be registered directly in the e-CRF by the investigator or a delegate.

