7.2 Exclusion criteria

- Molar pregnancy, multiple gestation or non-vital pregnancy
- Nausea and vomiting of other aetiology than NVP

CONFIDENTIAL

- Allergic to selective 5-HT3-receptor antagonists
- Ongoing treatment with antidepressant medication
- Pre-existing diagnosis of chronic kidney disease, diabetes type 1 or 2, significant cardiac disease (incl. long QT syndrome), epilepsy, HIV. In case of other pre-existing conditions subjects might be excluded based on individual assessment by an MD
- Elevated liver enzymes (ALAT/ASAT >150 U/l)
- Elevated creatinine (>100 µmol/l)
- ECG showing long QT-syndrome (QTc >460msek)
- Weekly alcohol intake >2 units of alcohol
- Not able to take medicine orally
- Not able to understand spoken and/or written Danish
- Participation in another investigational drug trial within current pregnancy

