7.4 Discontinuation

Subjects will be informed about the possibility of discontinuing the trial at any time. We will encourage the subjects to inform the investigator as soon as they have decided to discontinue the trial and last administration of trial medication will be registered. In case of discontinuation we will ask the subject to indicate a reason for the discontinuation which will be registered. If the reason for discontinuation is treatment failure, time of treatment failure will be registered.

Subjects will be discontinued from the trial in case of icterus or mania or if they comply with an exclusion criterion.

Subjects may be unblinded at discontinuation if this is necessary to make clinical decisions about their future treatment. Subjects will be encouraged to fill out daily online questionnaires on possible side effects until three days after last administration of trial medication.

Birth outcome will be registered on all subjects including dropouts unless subjects withdraw consent.

Data on treatment effect (NVP symptoms) collected before discontinuation will be evaluated and dropouts will not be replaced by new subjects.

All discontinued subjects will have to return the trial medication.

8. Randomisation, treatment blinding / unblinding and sample size

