14.2 Subject Discontinuation

The subject will be advised in the informed consent form that he/she has the right to withdraw from the trial at any time without prejudice. Where discontinuation from the trial is initiated by the subject, the investigator is to ascertain the primary reason for discontinuation from the list below:

- An AE for which the investigator did not consider discontinuation from the trial necessary
- Co-existing disease
- Withdrawal of consent
- Other reasons including treatment failure

The subject may at any time be discontinued from the trial at the discretion of the investigator.

Subjects must be discontinued from the trial under the following circumstances:

- If a criterion equivalent to an exclusion criterion occurs
- If, in the investigator's opinion, continuation in the trial would be detrimental to the subject's well-being
- Occurrence of intolerable AE(s) as determined by the investigator and/or subject
- Subject lost to follow-up
- If the randomisation code is broken
- If informed consent is withdrawn

In all cases, the primary reason for discontinuation must be recorded in the e-CRF and in the subject's medical records. Follow-up on the subject is necessary to establish whether the reason was an AE. If so, this must be reported in accordance with the appropriate procedures.

CONFIDENTIAL

As far as possible, all examinations scheduled for the final visit must be performed on subjects who receive the IMP but do not complete the trial according to the protocol.
 Data obtained until discontinuation will be entered in the clinical database and used for statistical analyses.

15. Administrative procedures

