- Change in EQ-5D (health-related quality of life) from baseline to Day 7(+/-1) and baseline to Day 14(+/-1) in the three different groups.
- Change in past 7 days PSQI (Pittsburg Sleep Quality Index) from baseline to Day 7(+/-1) and baseline to Day 14(+/-1) in the three different groups.
- Patient satisfaction with treatment VAS on Day 7(+/-1) and Day 14(+/-1) in the three different groups.

CONFIDENTIAL

- Change in patient consideration of termination of pregnancy from baseline to Day 7(+/-1) and baseline to Day 14(+/-1) in the three different groups.
- Frequency of and time to treatment failure in the three different groups.
- Frequency of request for dosage increase in the three different groups.
- Average daily use of rescue medication during the intervention in the three different groups.
- Number of days of sick leave during the intervention in the three different groups.
- Number of treatments with i.v.-fluids during the intervention in the three different groups.
- Number of days of hospitalizations during the intervention in the three different groups.
- Weight change in kg from baseline to Day 7(+/-1) and baseline to Day 14(+/-1) in the three different groups.
- Frequency of request for continuation of trial medication after end of intervention in the three different groups.
- Birth outcome (birth weight, gestational age, APGAR, umbilical cord pH, placenta weight, sex, hospitalizations on neonatal ward during the first month post-partum). This endpoint will not be double blind on all patients since patients can be unblinded after end of the intervention. The statistician will remain blinded.

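### Treatment failure is tied to the woman's own decision to leave, so a woman removed because worsening symptoms stop her taking oral medicine can go uncounted

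*Protocol*

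**What the plan says.** Protocol 10.17 gives a single trigger: "Treatment failure will be registered if a subject decides to discontinue the trial because of insufficient symptom relief". Protocol 14.2 has two lists. The first applies to the subject's own choice ("Where discontinuation from the trial is initiated by the subject, the investigator is to ascertain the primary reason for discontinuation from the list below") and includes treatment failure under other reasons. The second sets out when discontinuation is mandatory and does not mention treatment failure.

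The mandatory list includes "If a criterion equivalent to an exclusion criterion occurs". Protocol 7.4 has the same rule: "Subjects will be discontinued from the trial in case of icterus or mania or if they comply with an exclusion criterion". One exclusion criterion in 7.2 is "Not able to take medicine orally". The criteria are checked again at Visits 2 and 3 (10.1: "Re-assess compliance with inclusion and exclusion criteria").

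The SAP lists the endpoint in 9.1 ("Frequency of and time to treatment failure in the three different groups") and in 6.9 says only "Possible treatment failure will be registered when it occurs". It gives no definition of failure. SAP 9.2 and 9.3 give no method for time to failure and no rule for women who leave for other reasons.

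**The concern.** Protocol 6.2 introduces treatment failure while discussing drop-out and missing data. It is meant to retain information about effect when a woman leaves before Day 14. A woman whose symptoms worsen until she cannot swallow capsules is a clear case of what the endpoint should capture. Yet the rules direct her to a mandatory discontinuation, which is not the event in 10.17.

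Two things are at stake. Some efficacy-related failures may be missing from the endpoint, and the number missing may differ between arms. Sites may also classify the same clinical course differently, because no text says which route takes precedence when both apply.

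**Working it through.** **Reading the sections together**

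1. 10.17 requires that the subject decides to leave and that the reason is lack of relief.
2. 7.2 with 7.4 and 14.2: loss of oral intake requires discontinuation whether or not she decides to leave. The first condition in 10.17 then need not be met.
3. 7.4 asks a discontinuing subject for her reason and registers a time of failure if that reason is treatment failure. It does not expressly limit this to subject-initiated exits. 6.2 also says subjects are prompted to state whether lack of relief was why they dropped out. A removed woman who gives that reason could be registered.
4. 14.2 requires a primary reason for every discontinuation, so these women can be found in the data if the reason is coded specifically enough.

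**The plan's own figure**

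The documents give no rate or power for treatment failure. The only plan figure used here is the arm size. With a difference of 2, SD 3, two-sided alpha 2.5% and 80% power: 2 × [3 × (2.2414 + 0.8416) / 2]² = 42.77 per arm, and 42.77 / 0.75 = 57.03. The plan states 57 and rounds up to 60.

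**Illustration (all rates assumed)**

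Let the true failure risks be pP = 25% on placebo and pM = 10% on mirtazapine. Let sP and sM be the shares of failures that go uncounted. Then

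- recorded difference = pP(1 − sP) − pM(1 − sM)
- expected recorded counts = 60 × pP(1 − sP) and 60 × pM(1 − sM)

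| sP | sM | Counts, placebo v mirtazapine | Difference, points | Risk ratio |
|---|---|---|---|---|
| 0% | 0% | 15.0 v 6.0 | 15.0 | 2.50 |
| 25% | 25% | 11.25 v 4.5 | 11.3 | 2.50 |
| 50% | 50% | 7.5 v 3.0 | 7.5 | 2.50 |
| 50% | 25% | 7.5 v 4.5 | 5.0 | 1.67 |
| 50% | 0% | 7.5 v 6.0 | 2.5 | 1.25 |
| 25% | 50% | 11.25 v 3.0 | 13.8 | 3.75 |

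For the first three rows, power for a two-sided 5% comparison of proportions (pooled variance under the null) is 58.2%, 44.5% and 30.5%.

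**Direction**

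The recorded difference equals the true difference minus (pP·sP − pM·sM). At these risks it shrinks when 0.25·sP > 0.10·sM, that is, when sM < 2.5·sP. Above that it grows. If nothing is lost on mirtazapine, the ranking reverses only when 0.25(1 − sP) < 0.10, that is, when sP exceeds 60%.

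**The case against.** A failure endpoint based on the subject's own decision is a legitimate choice. The plan also has several means of keeping a worsening woman in the trial: repeat dosing after early vomiting, rescue medication by mouth or intravenously, an optional dose increase, and participation as an in-patient. Nothing says that brief intolerance meets the exclusion criterion, and a removal at Visit 3 cuts off little follow-up. Deterioration also shows in other secondary endpoints, and SAP 8.4 already reports the number, time and reason for discontinuation. All of this stands. It limits how often the gap matters but does not close it.

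A reader might infer more than the documents support:

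- **That every woman removed for loss of oral intake is uncounted.** Sections 6.2 and 7.4 allow some to be registered through their stated reason.
- **That such removals are frequent.** The remark in 6.2 that women with high PUQE-24 scores often cannot tolerate tablets explains the entry criteria. It gives no rate on treatment.
- **That a code break is a hidden failure.** Protocol 8.2 allows one for a medical emergency or when the woman's care requires it, and neither need mean lack of effect.
- **That these women are censored as if their exit were uninformative.** The SAP names no time-to-failure method. Simple censoring is possible but not stated.

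**Conclusion.** The gap is real and follows from the text. A discontinuation forced by worsening symptoms does not meet the definition in 10.17 unless the woman supplies the reason herself, and whether that suffices is left open. The endpoint can therefore miss severe failures and may be counted differently across sites.

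The absolute difference between arms is likely to be attenuated. On the assumed 25% and 10% risks, equal losses of 25% to 50% reduce it from 15.0 to between 11.3 and 7.5 points. The unequal losses tried give 2.5 to 13.8 points. It would be wrong to infer that the endpoint always understates benefit or that a reversal is to be expected. Equal proportional loss leaves the risk ratio unchanged, and a larger loss on mirtazapine can raise it (3.75 against 2.50 in the last row). Size and direction depend on how removals split between arms, for which the documents give no figure.

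This is one secondary endpoint with no role in the sample size. The coprimary PUQE-24 analysis does not use it.

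**What to change.** Change the endpoint definition and its coding, and leave every discontinuation rule as it is.

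1. In Protocol 10.17 and SAP 9.1, define treatment failure as discontinuation, initiated by the subject or the investigator, because symptom relief was inadequate. Include inability to take oral medicine attributed to nausea and vomiting of pregnancy. Include a code break only where the recorded reason is insufficient effect.
2. In Protocol 14.2 and the e-CRF, make this reason selectable for both kinds of discontinuation, and code it separately from the other exclusion criteria.
3. Report the subject-decided component separately, so the present definition remains visible.
4. In SAP 9.2, treat discontinuations for other reasons as competing events in the time-to-failure analysis.

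The cost is short edits to both documents and one e-CRF option. A primary reason is already required for every discontinuation, so little new data collection is needed. The downside is that the investigator must judge, while blinded, why the woman can no longer take oral medicine.
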